Recently a sponge on a string device has been studied in BE screening.(19) This device consists of a polyurethane foam sponge compressed in a vegetable material derived capsule, attached to a string. The capsule is swallowed by the patient. The shell of the capsule dissolves in the gastric fluid releasing the foam device as a sphere which is then pulled out with the attached string, providing brushing/cytology samples of the proximal stomach and esophagus. Biomarker studies can then be performed on these samples to detect BE. Two large multicenter studies have been performed in the United Kingdom with such a device using trefoil factor 3 (a protein specific to BE epithelium) detected on immunohistochemistry as a BE marker, demonstrating the feasibility, safety and accuracy of this approach. (19, 20) The sensitivity and specificity of this marker in the detection of BE has been reported to be 73% and 94% for BE segments of > 1 cm in circumferential length. Additionally this capsule sponge device has been used safely in a study conducted at Mayo Clinic Rochester in subjects with eosinophilic esophagitis.(21)

Methylated DNA markers specific to BE epithelium (with and without dysplasia) have been described by us and others.(22) We have identified several methylated DNA markers which are highly specific and sensitive for the detection of BE and BE related dysplasia/carcinoma (see preliminary data section).

An investigational capsule sponge device (SOS: EsophaCap) is currently available in the United States in two sizes (25 mm and 30 mm size) and two porosity configurations (10 pores per inch [ppi] and 20 pores per inch). There is currently no data on the optimal size and pore configuration in terms of DNA yield, patient tolerability and safety on this device.

The aims of our Phase 1 pilot study are:

- 1. Compare patient acceptance and tolerability with the 25 mm 10 ppi and 25 mm 20 ppi configurations capsule sponge devices.
- 2. Compare presence and degree of mucosal abrasions following swallowing and withdrawal of capsule sponge, as determined on endoscopy with the 25 mm 10 ppi and 25 mm 20 ppi configurations) capsule sponge devices
- 3. Compare DNA yield obtained from esophageal cytology specimens obtained with the 25 mm 10 ppi and 25 mm 20 ppi and capsule sponge devices.
- 4. Explore sensitivity and specificity of DNA methylation markers in detecting BE and BE related dysplasia.

Phase 2 Aims:

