- a. All participants will undergo a diagnostic clinically indicated sedated endoscopy within 24 hours of the Capsule sponge test. This will be performed in one of the clinical endoscopy units at Mayo Clinic Rochester, Mayo Clinic Florida, Mayo Clinic Arizona, Mayo Clinic Health Systems – Austin, Mayo Clinic Health Systems - Mankato, Northwell Health, and Baylor University Medical Center.
- b. Patients will receive sedation (using a combination of intravenous midazolam and Demerol) or monitored anesthesia care as clinically appropriate and undergo clinically indicated endoscopy with standard endoscopic equipment.
- i. The following landmarks will be identified, recorded (in centimeters from the incisors) and photographed: squamo-columnar junction, gastroesophageal junction (GEJ) (defined as top of the gastric folds with the esophagus partially deflated) and the diaphragmatic hiatus. Endoscopically suspected BE will be defined as the presence of ≥ 1cm of columnar mucosa above the GEJ. Targeted clinical biopsies will be obtained to confirm a diagnosis of BE. Presence of intestinal metaplasia with goblet cells will be a pre-requisite for the diagnosis of BE (histologically confirmed BE).
- ii. The presence or absence of esophagitis will be recorded. If present, esophagitis will be graded as per the LA classification.
- iii. The presence of any trauma from the passage of the sponge will be assessed and recorded photographically. This will be defined as:
 - 1. No evidence of trauma
 - 2. Superficial mucosal abrasion without bleeding
 - 3. Superficial mucosal tear abrasion with minimal oozing similar to that from biopsy.
 - 4. Deep mucosal abrasion without bleeding.
 - 5. Deep mucosal abrasion with greater than minimal oozing.
 - 6. Bleeding requiring endoscopic therapy.
- iv. In those with known BE, clinical surveillance biopsies (with or without endoscopic mucosal resection if clinically indicated for visible lesions) will be obtained as per current clinical recommendations: four quadrant biopsies every 1-2 cm. All clinical histology will be read by GI pathologists as per standard practice at Mayo Clinic Rochester, Mayo Clinic Florida, Mayo Clinic Arizona, or Mayo Clinic Health Systems. Slides or scanned slides from Northwell Health and Baylor University Medical Center

- will be sent to Mayo Clinic Rochester GI study Pathologist to confirm Barrett's Esophagus and dysplasia grade.

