A factorial design will be used to compare porosity of sponge 25 mm 10 pores per inch (PPI) vs. 25 mm 20 PPI, and Barrett's Esophagus vs. normal esophagus. Tolerability will be measured using a tolerability score as well as level of mucosal abrasion (scale 0-6, 6=worst). The assumed standard deviation for the tolerability score of 2.2 was obtained from Sami, et al.. Using a two-sided test of significance of 5% and 80% power, we can detect a minimal shift in tolerability score of at least 2. For mucosal abrasion score, a rough estimate of 1 standard deviation (s.d. ≈ range of data / 4) will be used and assuming a two-sided test of significance of 5% we have 86% power to detect a difference in mean mucosal abrasion score of at least 1. DNA yield will be measured using wild type Beta-actin. Using a two-sided test of significance of 5% we have 82% power to detect a fold change difference of 50%. All above power calculations are based on detection of main effect comparisons with n=20 per group. The ability to detect interactions between main effects will be very limited with the given sample size. Recruitment will continue until 40 individuals have successfully completed the sponge procedure using the

25 mm sponge. We anticipate 25% will decline swallowing sponges after they have consented, therefore the total number of people we anticipate recruiting will be set at 60.

Phase 2: For the detection of Barrett's Esophagus, sample size justification will be based on minimizing the width of the 95% confidence interval of the sensitivity for detecting Barrett's Esophagus with a fixed specificity of 90%. From table 2 below, based on various assumed sensitivities, the largest confidence interval width for the proposed sample size is less than ±9%. Similarly for detection of dysplasia among Barrett's Esophagus patients, the largest width for the proposed sample size is less than ±12. These confidence widths are reasonable for this initial feasibility study. We also intend to perform multivariable modeling using machine learning techniques to evaluate a minimum of 14 methylation markers. Using the rule of thumb for machine learning of 10-15 events per marker, a minimum of 140 to 210 cases and an equal number of controls is required (total 280 to 420 patients) to account for assay failures and indeterminate histological findings on endoscopic exam. We anticipate enrolling up to 1000 participants.

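### The Phase 1 abrasion power of 86% is right for SD = 1, but the plan's range/4 rule needs a 4-point range that neither of its two conflicting abrasion scales supplies

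*Combined protocol and SAP*

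**What the plan says.** In the combined protocol and SAP, the Phase 1 part of 'Sample size and Statistical analysis' describes the outcome as "mucosal abrasion (scale 0-6, 6=worst". For its variability the plan says "a rough estimate of 1 standard deviation (s.d. ≈ range of data / 4) will be used", and it concludes that "we have 86% power to detect a difference in mean mucosal abrasion score of at least 1", at a two-sided 5% level. It adds that "All above power calculations are based on detection of main effect comparisons with n=20 per group".

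The section 'Endoscopic assessment' (item iii under C) defines the same assessment as a list of six categories. Number 1 is "No evidence of trauma" and number 6 is "Bleeding requiring endoscopic therapy". There is no category 0 and no seventh category.

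For the other Phase 1 score the plan names a source: "The assumed standard deviation for the tolerability score of 2.2 was obtained from" a cited study. The abrasion SD has no source beyond the range rule. The background section says of the device: "There is currently no data on the optimal size and pore configuration in terms of DNA yield, patient tolerability and safety on this device".

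**The concern.** The power statement takes its SD from a rule whose input, the range, is not stated. The only ranges that can be read from the document are 6 and 5, and neither gives SD = 1 when divided by 4. The two scales also disagree with each other: six defined categories cannot fill a scale that runs from 0 to 6.

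Abrasion is not incidental in Phase 1. Comparing it between the two sponges is the second Phase 1 aim, and under 'Study Design' mucosal irritation is one of four criteria for choosing the sponge used in Phase 2. A non-significant abrasion comparison would naturally be read against the 86%. If the SD were 1.25 or 1.5, that reading would be too reassuring.

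**Working it through.** **Inputs.** From the Phase 1 sample size text: n = 20 per group, two-sided 5%, difference 1, SD 1. From the same text: a 0-6 scale. From 'Endoscopic assessment': categories 1 to 6. The planned test is analysis of variance, which for a two-level factor is essentially the two-sample t-test.

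**Method.** Power comes from the noncentral t distribution with 38 df, noncentrality = difference / (SD × √(2/20)) and critical value t(0.975, 38) = 2.024.

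**Check on the method.** For tolerability (SD 2.2, difference 2) it gives 80.0%, matching the plan's 80%.

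**The plan's own abrasion figure.** With SD 1 and difference 1, noncentrality = 1 / (1 × 0.316) = 3.16 and power = 86.9%. With the 36 error df of the 2×2 layout it is 86.8%. The stated 86% is reproduced. The SD that gives exactly 86% is 1.014, which confirms that an SD of about 1 was used.

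**The step from range to SD.** SD = 1 requires range = 4 × 1 = 4.

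- Scale 0-6: range 6 − 0 = 6, SD = 6/4 = 1.5.
- Categories 1-6: range 6 − 1 = 5, SD = 5/4 = 1.25.

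**Sensitivity to the range** (n = 20 per group, two-sided 5%, 38 df). The CI half-width is 2.024 × SD × √(2/20).

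| Points spanned by scores | SD = range/4 | Power for 1 point | Difference detectable with 80% power | Difference detectable with 86% power | 95% CI half-width |
|---|---|---|---|---|---|
| 3 | 0.75 | 98% | 0.68 | 0.74 | 0.48 |
| 4 | 1.00 | 87% | 0.91 | 0.99 | 0.64 |
| 5 | 1.25 | 69% | 1.14 | 1.23 | 0.80 |
| 6 | 1.50 | 54% | 1.36 | 1.48 | 0.96 |

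The rows for 5 and 6 points assume that scores cover the whole of one or other documented scale. They are conditional results, not forecasts. Under the rule, power for 1 point stays at 86% or more only if the span is at most about 4.05 points (4 × 1.014), and at 80% or more only up to about 4.40 points (4 × 1.100).

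**The case against.** The best reply is that the rule refers to the range of the data, not of the scale. If the worst category were not seen among the 40 completers, the six categories would reduce to five. The range would then be 4 and the SD exactly 1. The exclusions make this plausible: bleeding diatheses, known varices or cirrhosis, and several kinds of anticoagulant or antiplatelet use. So does the background's account of earlier studies of a similar device as showing safety. This stands, and it is why SD = 1 cannot be called wrong. It does not supply what is missing, because the plan neither states this reasoning nor gives an expected range.

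It can also be said that the numbers in 'Endoscopic assessment' are only list numbering, and that a shift of origin (0-5 instead of 1-6) changes neither an SD nor a mean difference. That is true, provided everyone codes alike. It does not settle whether there are six or seven levels, and the rule gives a different SD for each.

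Thirdly, the plan discloses SD, difference, level and n, and calls the SD rough, so a reader can see that about one SD is detectable and can rescale. That also stands. What the reader lacks is a basis for how many scale points one SD represents.

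Finally, this is a pilot. The sponge is chosen on four criteria together, no significance rule is set for abrasion, and abrasion is also summarised by median and interquartile range. This limits the consequence but does not remove the inconsistency.

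**Conclusion.** The point holds in a limited form. The 86% is arithmetically correct for SD = 1. SD = 1 does not follow from the plan's own rule on either scale it documents, and those two scales contradict each other. The assumption is unsupported, not disproved.

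A reader might infer that the power was miscalculated, or that true power is 54% or 69%. The document supports neither. The calculation reproduces, and the lower figures hold only if scores span the full scale; if scores cluster in the low categories, power could exceed 86%. A reader might also infer that Phase 1 needs more patients. That would follow only if a full-scale SD were established and 86% power for 1 point were required, and the plan establishes no such SD.

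The size of the problem is the spread in power for 1 point, from 87% down to 54% as the span goes from 4 to 6 points, or equally a detectable difference at 80% power of 0.91 to 1.36 points. It affects how the Phase 1 abrasion comparison is read. The sample size and the sizing of Phase 2 are not affected. The figures assume 20 completers per group and a t-test or its ANOVA equivalent.

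**What to change.** 1. Use one abrasion scale in 'Endoscopic assessment' and in the Phase 1 sample size text, with every level defined. If 0-6 is kept, seven definitions are needed.

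2. Restate the power sentence with the range it rests on and its sensitivity, keeping the rows that the chosen scale allows. For example: *With n = 20 per group and a two-sided 5% test, the difference detectable with 80% power is 0.91 points if scores span 4 points (SD 1; power for 1 point 87%), 1.14 if they span 5 (SD 1.25; 69%), and 1.36 if they span 6 (SD 1.5; 54%).*

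3. Keep 86% as the main figure only if a basis is given for a 4-point range, such as the categories expected to occur, or if another source for SD = 1 is named.

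The cost is one scale label and one sentence. No patients, procedures or Phase 2 plans change. The only drawback is a less favourable stated figure if no basis for the 4-point range can be given.

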In addition, clinically archived FFPE tissue from up to 10 cases will be used to assess methylated DNA marker levels in biopsies versus the sponge.

Due to the known dysplasia miss rate with routine surveillance endoscopy, we hypothesize that there will be undetected or missed dysplasia in BE patients with a negative surveillance histology. This imperfection in the endoscopic "gold" standard will bias the resulting accuracy estimates of methylation markers in a multitude of ways. There are several approaches in the literature to address this issue; all with their own caveats. The three approaches that will be investigated are latent class analysis, Bayesian estimation, and discrepant resolution. We have hence inflated the sample size estimates in table 2 to correspond with a 30% prevalence of undetected dysplasia in those with no dysplasia on conventional surveillance endoscopy to ensure that we have 50 true BE subjects without dysplasia.

Table 2

	BE vs. No BE			BE no dysplasia vs. BE w/dysplasia				
Confidence Level	0.95	0.95	0.95	0.95	0.95	0.95	0.95	0.95
Sensitivity	0.75	0.80	0.85	0.90	0.75	0.80	0.85	0.90
Confidence bands	0.085	0.078	0.070	0.059	0.105	0.097	0.087	0.073
N no BE/BE without dys/BE with dys	100	100	100	100	65	65	65	65

Statistical analysis

Phase 1: Tolerability score and level of mucosal abrasion will be summarized as median and interquartile range. Analysis of variance will be used to detect statistically significant differences in tolerability score and level of mucosal abrasion between different levels of sponge porosity and size. Failure/complication rate will be summarized as the percentage of the group total. Comparisons between sponge porosity and size for failure/complication rate will be analyzed using the Chi-squared test.

Phase 1 and 2: Marker specificity will be defined as the 90th percentile value in subjects without BE. Several markers will be combined based on the coefficients from a logistic regression model using subjects with BE vs subjects without BE as the response. This approach is used as they represent the broadest spectrum of disease and any marker combination that fails to discriminate between these two subgroups would not be of future value. The specificity of the combined markers will then be set equal to the 90th percentile in non-BE subjects. The corresponding sensitivity of individual markers as well as combined markers will be estimated with 95% confidence intervals.

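### Table 2 gives the precision of sensitivity at a cut-off known in advance, not at 90% specificity with the cut-off estimated from the study's own controls

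*Combined protocol and SAP*

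**What the plan says.** The Phase 2 paragraph of *Sample size and Statistical analysis* bases the sample size on "minimizing the width of the 95% confidence interval of the sensitivity for detecting Barrett's Esophagus with a fixed specificity of 90" per cent. It reads two bounds from Table 2. For BE against no BE, "the largest confidence interval width for the proposed sample size is less than ±9"%. For dysplasia among BE patients, "the largest width for the proposed sample size is less than ±12". It judges these widths acceptable for a feasibility study.

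Table 2 lists half-widths for sensitivities 0.75 to 0.90 with N = 100 and N = 65, in a row labelled "N no BE/BE without dys/BE with dys".

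The same paragraph gives a second sample-size argument from the number of events per marker: "a minimum of 140 to 210 cases and an equal number of controls is required". It expects to enrol up to 1000 people.

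Under *Statistical analysis, Phase 1 and 2*, the cut-off comes from the study data. For single markers, "Marker specificity will be defined as the 90th percentile value in subjects without BE". For panels, "Several markers will be combined based on the coefficients from a logistic regression model using subjects with BE vs subjects without BE", and then "The specificity of the combined markers will then be set equal to the 90th percentile in non-BE subjects". The dysplasia analysis follows the same steps with non-dysplastic BE subjects as controls. Sensitivities are to have 95% confidence intervals, but no interval method is named. Neither section gives an external or pre-locked cut-off.

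**The concern.** Sensitivity at 90% specificity depends on two samples. The cases show what fraction exceeds the cut-off, and the controls show where the cut-off lies. A binomial width uses only the first. If the 90th percentile of 100 or 65 controls lands too high or too low, the estimated sensitivity moves with it, and Table 2 does not count that movement.

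Two things are at stake. The widths are one of the two arguments for the Phase 2 size, and they answer a different question from the one the text poses. Also, because no interval method is named, the results for Phase 2 aims 1 and 2 could be reported with the same type of interval, which would usually be too narrow for sensitivity at 90% specificity.

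**Working it through.** **Inputs from the documents.** Sensitivities p = 0.75, 0.80, 0.85, 0.90; 95% confidence; specificity 0.90; N = 100 and 65 (Table 2); 140 to 210 per group (Phase 2 text); biopsy quartiles (Table 1 of *Preliminary Data*).

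**Step 1: reproduce Table 2.** Half-width = 1.96·√(p(1−p)/N).
- N = 100: 0.0849, 0.0784, 0.0700, 0.0588 (printed 0.085, 0.078, 0.070, 0.059).
- N = 65: 0.1053, 0.0972, 0.0868, 0.0729 (printed 0.105, 0.097, 0.087, 0.073).

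All eight match. No control-sampling term enters.

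**Step 2: add the cut-off term.** With n₁ cases, n₀ controls and the cut-off at the empirical 90th percentile of the controls:

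half-width = 1.96·√( p(1−p)/n₁ + s²·0.09/n₀ )

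Here s is the ROC slope at the cut-off (case density divided by control density), and 0.09 = 0.90 × 0.10. The added term is positive whatever the marker distribution. Its size needs s, which the documents do not give.

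**Step 3: assume a binormal marker** with r = case SD / control SD. Then s = φ(z_p)/(r·φ(1.2816)). At p = 0.75, s = 3.018, 2.012, 1.811, 0.905, 0.604 for r = 0.6, 0.9, 1, 2, 3.

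Example, 100/100 and r = 1: 0.1875/100 + 1.811² × 0.09/100 = 0.001875 + 0.002952 = 0.004827. The square root is 0.0695, and × 1.96 gives 0.136.

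Half-widths in percentage points at p = 0.75:

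| Cases/controls | r = 0.6 | 0.9 | 1 | 2 | 3 | Printed |
|---|---|---|---|---|---|---|
| 100/100 | 19.7 | 14.6 | 13.6 | 10.0 | 9.2 | 8.5 |
| 130/100 | 19.2 | 14.0 | 13.0 | 9.2 | 8.2 | 8.5 |
| 65/65 | 24.4 | 18.1 | 16.9 | 12.4 | 11.4 | 10.5 |
| 140/140 | 16.6 | 12.3 | 11.5 | 8.5 | 7.8 | – |
| 210/210 | 13.6 | 10.0 | 9.4 | 6.9 | 6.3 | – |

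The 130/100 row is there because the N label can be read as 65 + 65 = 130 BE cases against 100 without BE. The printed 8.5 uses N = 100; with N = 130 the binomial width alone would be 7.4. At p = 0.90 and r = 1 the half-widths are 8.3 (100/100; printed 5.9) and 10.3 (65/65; printed 7.3).

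**Step 4: where the stated bounds are met** (p = 0.75). ±9% needs r above about 3.6 (100/100), 2.1 (130/100), 1.7 (140/140) or 1.1 (210/210). ±12 needs r above about 2.3 (65/65).

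**Step 5: what the documents show about r.** SD on the log scale is taken as ln(Q3/Q1)/1.349.
- BMP3 composite: control ln(3.8/0.4)/1.349 = 1.669; case ln(242.7/67.1)/1.349 = 0.953; r = 0.57.
- NDRG4 composite: 1.166 and 1.019; r = 0.87.
- BE tissue against control squamous or cardia: 0.79 to 0.98.

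These are biopsies with near-complete separation and may not transfer to sponge samples.

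**Step 6: simulation of a single marker** (20,000 replicates, p = 0.75). For r = 0.6, 0.9, 1, 2, 3, 1.96·SD is 0.188, 0.141, 0.132, 0.099, 0.091 at 100/100, so the formula runs slightly high at low r. Coverage of sensitivity at 90% specificity by a nominal 95% Wald interval:
- 100/100: 60, 74, 77, 90, 93%.
- 65/65: 58, 72, 76, 88, 91%.
- 210/210: 59, 74, 77, 89, 92%.

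For sensitivity at the cut-off actually observed, the same intervals cover about 93 to 95%. The true specificity there is not fixed, however: its 95% range is about 0.825 to 0.945 with 100 controls and 0.80 to 0.95 with 65.

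**Step 7: intervals that work.** A single-marker bootstrap that re-derives the cut-off covers 94 to 97% at 100/100, 130/100 and 65/65.

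Panels were simulated with 14 equal, independent normal markers and a logistic fit, at 65, 100, 140 and 210 per group. Coverage of the fitted panel's true sensitivity was:
- re-fitting and scoring on the same resample: 22, 41, 58, 67%;
- cross-validated scores with a Wald interval: 74, 74, 76, 77%;
- cross-validated scores with a bootstrap that re-derives the cut-off: 93, 93, 95, 94%.

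The last method gave 93 to 96% in 12 further settings. Marker selection and machine-learning tuning were not simulated.

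**The case against.** - **Enrolment may be much larger.** At 500/500 the formula gives ±8.8 points even at r = 0.6, and ±6.1 at r = 1. This stands as a point about achievable precision. However, 1000 is a ceiling with no case/control split, the quoted bounds are tied to 100 and 65, and larger equal groups do not restore coverage.
- **Low r does not belong with sensitivity 0.75.** The biopsy data that give r = 0.57 and 0.87 also imply a sensitivity near 0.997. There the cut-off term hardly matters: about 1.3 and 1.1 points with it, 1.1 and 1.0 without, at 100/100. They also compare BE with non-BE tissue and say nothing about dysplasia. This is fair: the low-r columns show a range, not an expectation.
- **Dysplasia controls are impure.** The plan assumes 30% undetected dysplasia among apparent controls, so a clean two-group 65/65 width is not exact either. That is true, but it does not support the printed figure.
- **The binomial width is legitimate at the observed cut-off.** That is correct, but it is not the quantity the sample-size text names, and specificity would then need its own interval.
- **Under-coverage is conditional.** It follows only if Wald-type intervals are used, and at r = 3 the shortfall is small (91 to 93%). This stands. The plan's silence on method leaves the risk open.
- **Cross-validation addresses a separate problem, fitting optimism.** That is partly so, and it is one reasonable choice among several. But an interval method for panels has to handle both problems.

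**Conclusion.** The concern holds. Table 2's arithmetic is correct as binomial widths, but they are not the precision of sensitivity at 90% specificity under the planned analysis. For any given group sizes, the omitted variance term is positive. Against the printed figures, the direction is certain only if the groups are 100/100 and 65/65; at 130/100 and r = 3 the width is slightly below the printed one.

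The size rests on an assumed binormal marker, an assumed SD ratio and the least favourable sensitivity column (0.75). For r from 1 to 3, half-widths are 13.6 to 9.2 points rather than 8.5 (100/100), and 16.9 to 11.4 rather than 10.5 (65/65). On these assumptions ±9% is missed throughout that range at 100/100, while ±12 is met at 65/65 above r of about 2.3. Confidence is high that the term is missing and low about its exact size. This should be fixed, but it does not undermine the study: the enrolment the plan foresees may well reach the stated precision.

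**What to change.** 1. **Table 2 and both bounds.** State the case and control numbers for each comparison. Then either restate the half-widths with the cut-off term, as ranges labelled with the assumed SD ratios (including ratios below 1), or add a sentence such as: *These half-widths apply to a cut-off fixed in advance; they are not the precision of sensitivity at 90% specificity when the cut-off is estimated from study controls.*
2. **Single markers.** Specify a percentile bootstrap that resamples cases and controls separately and re-derives the 90th-percentile cut-off in each resample.
3. **Combined markers.** Do not re-fit and score the panel on the same resample. Report cross-validated sensitivity, with coefficients and any marker selection or tuning derived inside each fold. For the interval, bootstrap the out-of-fold scores of cases and controls separately, re-deriving the cut-off each time.

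The cost is one table or one qualifying sentence, two revised sentences on the bounds and two sentences in the analysis section. The stated precision becomes less favourable and the analysis takes slightly more work. No extra patients are needed.

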Marker specificity will be defined as the 90th percentile value in subjects with BE and no dysplasia. Several markers will be combined based on the coefficients from a logistic regression model using BE subjects with dysplasia vs subjects without dysplasia as the response. This approach is used as they represent the broadest spectrum of disease and any marker combination that fails to discriminate between these two subgroups would not be of future value. The specificity of the combined markers will then be set equal to the 90th percentile in BE subjects without dysplasia. The corresponding sensitivity of individual markers as well as combined markers will be estimated with 95% confidence intervals.

The association of demographic (age, gender, race), anthropometric (body mass index, waist hip ratio) and circulating biomarker levels (leptin, interleukins) with a BE diagnosis will be assessed using univariate and multivariable logistic regression analysis.

References:

- 5. Fitzgerald RC, di Pietro M, Ragunath K, et al. British Society of Gastroenterology guidelines on the diagnosis and management of Barrett's oesophagus. Gut 2014;63:7-42.
- 9. Phoa KN, van Vilsteren FG, Weusten BL, et al. Radiofrequency ablation vs endoscopic surveillance for patients with Barrett esophagus and low-grade dysplasia: a randomized clinical trial. JAMA 2014;311:1209-17.

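### Phase 2's requirement of 280–420 patients contains no allowance for failures and sizes one of two marker panels; Table 2's apparent 65 dysplasia cases fall short of the plan's own events-per-marker rule

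*Combined protocol and SAP*

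**What the plan says.** The Phase 2 paragraph of Sample size and Statistical analysis first justifies the sample by confidence-interval width (Table 2). It then adds a second basis: multivariable modelling to "evaluate a minimum of 14 methylation markers". "Using the rule of thumb for machine learning of 10-15 events per marker", it arrives at "a minimum of 140 to 210 cases and an equal number of controls is required (total 280 to 420 patients) to account for assay failures". The same sentence names indeterminate histology as a second reason. The next sentence reads "We anticipate enrolling up to 1000 participants". No loss rate, split by group or derivation of that ceiling is given.

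The Statistical analysis section, under Phase 1 and 2, specifies two marker combinations. The first takes "coefficients from a logistic regression model using subjects with BE vs subjects without BE as the response". The second is fitted within BE, "using BE subjects with dysplasia vs subjects without dysplasia as the response". They serve separate aims (Phase 2 aims 1 and 2). The plan does not say how the 14 or more markers divide between the two.

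Table 2 sizes the groups for precision, with 100 under the BE contrast and 65 under the dysplasia contrast.

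**The concern.** A total described as covering failures should be larger than the evaluable number the rule produces, and this one is not. A total built from one set of cases and matching controls also cannot be read directly as the need of two models whose cases differ. In the first model a case is any BE patient. In the second it is a BE patient with dysplasia, and the controls are themselves BE patients.

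At stake is the dysplasia panel. The trial could reach its printed requirement, or its enrolment ceiling, with too few dysplasia cases to satisfy its own rule, and no stated target would show this during recruitment.

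**Working it through.** **Inputs.** At least 14 markers, 10–15 events per marker, equal controls, and a ceiling of 1000 (Phase 2 sample size paragraph). Four named BE genes (Biomarker assays). Twelve dysplasia genes, two of which, BMP3 and NDRG4, are also among the four (Preliminary Data, dysplasia brushing study). The union is 12 + 4 − 2 = 14 genes. The dysplasia group size of 65 is my reading of Table 2.

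**1. The plan's figure.** Cases: 14 × 10 = 140 and 14 × 15 = 210. Total: 2 × 140 = 280 and 2 × 210 = 420. The match is exact, so inflation is zero. The documents give no failure rate. Under assumed losses, 280 and 420 would leave these events per marker:

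| Assumed loss | From 280 | From 420 |
|---|---|---|
| 5% | 9.5 | 14.25 |
| 10% | 9.0 | 13.5 |
| 20% | 8.0 | 12.0 |

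**2. One contrast or two.** I take the rule to apply to both panels, since the analysis section describes no other marker modelling.
- If cases means BE, there are 140–210 BE patients in all. An equal split by dysplasia (an assumption, in line with the equal-controls rule) gives 70–105 dysplasia cases: 70/14 = 5.0 to 105/14 = 7.5 per marker.
- If cases means dysplasia, the equal controls are BE patients without dysplasia, and the total holds no non-BE group.

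Neither reading serves both panels at 14 markers.

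**3. Need of the dysplasia panel.**
- All 14 markers as candidates: 140–210 dysplasia cases.
- Only the 12 dysplasia genes: 12 × 10 = 120 to 12 × 15 = 180.

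**4. What Table 2 offers.** The half-width 1.96 × √(p(1 − p)/n) at p = 0.75 is 0.085 for n = 100 and 0.105 for n = 65, as printed. The other six entries also reproduce. This supports reading 65 as the number of dysplasia cases on which sensitivity is estimated. Events per marker: 65/14 = 4.6 and 65/12 = 5.4.

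**5. Total over three groups** (no BE; BE without dysplasia; BE with dysplasia). It depends on the reading:

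| Reading | Evaluable total |
|---|---|
| 14 markers in both panels, three equal groups (BE to no BE 2:1) | 3 × 140 = 420 to 3 × 210 = 630 |
| 14 markers in both panels, no-BE controls equal to all BE cases | 4 × 140 = 560 to 4 × 210 = 840 |
| 4 BE markers, 12 dysplasia markers | 40 + 120 + 120 = 280 to 60 + 180 + 180 = 420 |

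**6. Against the ceiling.** 1000 leaves room for losses of 58% to 37% against 420–630, and of 44% to 16% against 560–840.

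**The case against.** The best defence on the allowance is a misplaced full stop: the requirement is 280–420, and enrolment rises to 1000 to cover failures. That is plausible, and the allowance would then lie in the step to 1000. It still leaves no loss rate, so the step cannot be checked.

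A reader might infer that the plan's rule fixes the need at 420–630, half as much again as printed. The documents do not support this. It assumes all 14 markers enter both panels, and it accepts a 2:1 BE to no-BE ratio although the text asks for equal controls. The 4-and-12 split even returns 280–420. Its composition, however, is not the printed one, and its 40–60 non-BE subjects fall below Table 2's 100.

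A reader might also infer that 1000 is too few. That is not shown: every total above lies below it, although 840 leaves only 16% for losses. Nor does the plan assume a loss of 58–72%, the gap between 280–420 and 1000; that treats a ceiling as a forecast. The 25% in Phase 1 concerns people who decline to swallow the sponge, and the 30% undetected dysplasia is applied to Table 2 only. Neither is a Phase 2 assay-failure rate.

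Finally, recruitment is not wholly untied from dysplasia. The Participants section enriches for it, and the Phase 2 aims section says recruitment will be monitored. Neither gives a number. It is also fair that the rule of thumb is secondary to the precision argument in early feasibility work. That limits the consequence but does not reconcile 65 with 120–210.

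**Conclusion.** The point holds in limited form. It is certain that 280–420 carries no allowance and that, as described, it sizes one contrast while two are planned. The shortfall for the dysplasia panel holds on both marker counts considered: 120–210 cases by the plan's rule against an apparent 65, or 4.6–5.4 events per marker instead of 10–15. This rests on reading Table 2's 65 as the dysplasia group and on applying the rule to both panels. More than 14 markers would widen the gap.

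The overall total is not determined by the documents (280–840 across the readings). The gap is in group composition and in the derivation of 1000. It should be corrected, because a stated basis for sample size is not delivered for one of the two panels.

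**What to change.** In the Phase 2 sample size paragraph:

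- State the number of candidate markers for each panel.
- Replace the single total with evaluable targets for no BE, BE without dysplasia and BE with dysplasia. With all 14 markers in both panels and a 2:1 BE to no-BE ratio accepted, these are 140–210 each, 420–630 in all. If controls must equal all BE cases, the total is 560–840.
- Reconcile the dysplasia target with Table 2's 65.
- Give the assumed rate of assay failure and indeterminate histology as a separate factor, and show how it leads to 1000. If the phrase about failures was meant to explain that step, correct the punctuation.
- Monitor recruitment against the three group targets.
- If the dysplasia group will not reach its target, either say that the 10–15 rule is met for the BE panel only, or reduce the candidate markers for the dysplasia panel to suit the cases available.

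The cost is protocol wording and a less favourable stated requirement. None of the evaluable totals exceeds the 1000 already anticipated, but the top of the 560–840 reading fits only if losses stay at or below 16%.
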